5. GENERAL METHODOLOGY AND CONVENTIONS

The final analysis and reporting of results will be performed after the completion of the study and the database is locked. Interim analyses of data may be performed from time to time, see [Section 7](#).

5.1. Hypotheses and Decision Rules

Efficacy analyses will be descriptive in nature; there will be no formal hypothesis testing, though 95% two-sided confidence intervals will be reported. All the safety data will be summarized descriptively.

5.2. General Methods

In general, for descriptive analyses, number and percentage will be presented for binary variables. Number and percentage will be presented for categorical variables. Number, mean, median, standard deviation, minimum and maximum will be presented for continuous variables.

5.3. Methods to Manage Missing Data

In general, for analyses using descriptive statistics, missing values will not be imputed. In addition, for safety endpoints, missing values will not be imputed. Other methods for handling missing values are discussed below.

5.3.1. Patient/Observer Reported Outcomes Endpoints

For the continuous patient/observer reported outcomes variables, rules suggested by the developers of these instruments will be followed in calculating the missing values. If these rules are not enough for imputing a value, then the missing values will be treated as missing.

5.3.2. Concentrations Below the Limit of Quantification

In all data presentations (except listings), concentrations below the limit of quantification (BLQ) will be set to zero (In listings BLQ values will be reported as “<LLQ”, where LLQ will be replaced with value for the lower limit of quantification).

5.3.3. Deviations, Missing Concentrations and Anomalous Values for Pharmacokinetics

In summary tables, statistics will be calculated having set concentrations to missing if one of the following cases is true:

- A concentration has been collected as ND (ie, not done) or NS (ie, no sample);
- A deviation in sampling time is of sufficient concern or a concentration has been flagged anomalous by the pharmacokineticist.

Note that summary statistics will not be presented at a particular time point if more than 50% of the data are missing.

6. ANALYSES AND SUMMARIES

The primary endpoint of incidence of AEs will be analyzed using descriptive measures such as percentages along with confidence intervals. No statistical hypotheses will be tested. There is no pre-specified estimand for the safety evaluation and all the safety data will be summarized descriptively through appropriate data tabulations, descriptive statistics, and graphical presentations.

There is no pre-specified estimand for the efficacy and patient/observer reported outcomes evaluation. Efficacy and patient/observer reported outcomes analyses will be descriptive in nature; there will be no formal hypothesis testing, though 95% two-sided confidence intervals will be reported.

There is no pre-specified estimand for the PK evaluation. Predose (C_{trough}) plasma concentrations of crisaborole and its identified main oxidative metabolites (AN7602 and AN8323) will be listed and descriptively summarized, respectively.

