## **Statistical Methods**

The primary endpoint of incidence of safety events will be analyzed using descriptive measures such as percentages and exposure-adjusted incidence rates along with confidence intervals. No statistical hypotheses will be tested.

All the safety data will be summarized descriptively through appropriate data tabulations, descriptive statistics, and graphical presentations.

Efficacy analyses will be descriptive in nature; there will be no formal hypothesis testing, though 95% two-sided confidence intervals will be reported.

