##### **9.4.2. Primary Endpoint(s)**

The primary endpoint of incidence of safety events will be analyzed using descriptive measures such as percentages and exposure-adjusted incidence rates along with confidence intervals. No statistical hypotheses will be tested.

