1. VERSION HISTORY

Table 1. Summary of Changes

Version/ Date	Associated Protocol Amendment	Rationale	Specific Changes
1 4 Aug 2020	Original 20 May 2020	N/A	N/A
2 7 Jan 2021	Original 20 May 2020	Study termination	Updated the following analyses due to the small sample size and the short exposure period. 6.4. Subset Analyses 6.5.3. Study Treatment Exposure 6.5.4. Concomitant Medications and Nondrug Treatments 6.6.1. Adverse Events

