6.1. Primary Endpoint(s)

6.1.1. Primary Analysis

- Analysis Set: Safety analysis set (see [Section 4](#)).

- Analysis Methodology: Descriptive statistics (see [Section 5.2](#)) for incidence of TEAEs and SAEs

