6.6.1. Adverse Events

The safety data will be summarized in accordance with CaPS. All safety data will be summarized descriptively through appropriate data tabulations, descriptive statistics, categorical summaries, and graphical presentations. The subgroup analysis by age (<18, ≥18) will be conducted, where appropriate. Safety endpoints for the study include:

- Treatment-emergent AEs and SAEs;
- Withdrawals from active treatment due to AEs;

TEAEs and SAEs occurred in the treatment area will be summarized. Location of skin lesions will be listed.

It should be recognized that most studies are not designed to reliably demonstrate a causal relationship between the use of a pharmaceutical product and an adverse event or a group of adverse events. Except for select events in unique situations, studies do not employ formal adjudication procedures for the purpose of event classification. As such, safety analysis is generally considered as an exploratory analysis and its purpose is to generate hypotheses for further investigation.

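### The primary safety percentage has no single denominator or event window: SAP Section 4 can count participants who were never dosed, and SAP 3.5.1 ends the treatment-emergent window at two different times

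*SAP*

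**What the plan says.** **Measure.** Protocol 9.4.2 plans "descriptive measures such as percentages and exposure-adjusted incidence rates along with confidence intervals" for the only primary endpoint, and the synopsis agrees. SAP Section 6 reads "The primary endpoint of incidence of AEs will be analyzed using descriptive measures such as percentages along with confidence intervals", which keeps the percentages and intervals but not the rates. SAP 6.1.1 applies descriptive statistics "for incidence of TEAEs and SAEs" in the safety analysis set and refers to 5.2, where "number and percentage will be presented for binary variables" and no interval is listed. The 95% two-sided level is attached to efficacy and patient/observer outcomes (SAP 5.1 and 6). For safety, 5.1 says only: "All the safety data will be summarized descriptively". SAP 6.6.1 adds: "The safety data will be summarized in accordance with CaPS". That standard is not among the documents.

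**Denominator.** Protocol 9.3 defines the safety set as everyone with at least one dose. SAP Section 4 repeats this and then also includes participants entering a first Off-Treatment cycle.

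**Window.** SAP 3.5.1 flags as TEAEs the events that start from first dosing in this study up to end of study. The same section makes a TEAE depend on starting within the effective duration of treatment, which stops at last dose plus a lag. No lag value is given.

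**Version history.** SAP version 2 followed termination of the study: "Updated the following analyses due to the small sample size and the short exposure period". The sections listed are 6.4, 6.5.3, 6.5.4 and 6.6.1. Sections 3.5.1, 4, 6.1.1 and the opening of 6 are not listed.

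**The concern.** A single-arm descriptive safety study stands on its percentages: who is counted, over what time, and with what interval. Here two programmers could follow the SAP faithfully and produce different primary tables from the same database.

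The denominator problem runs in one direction. Someone who never receives the ointment in this study cannot contribute a TEAE but can be counted as event-free, so the percentage can only fall. The window problem can change the numerator. Off-Treatment cycles are part of the design, so a participant's last dose may come well before the last contact, and events in between count under one rule and not under the other. In the small sample left after termination, moving one or two participants changes the reported figure visibly.

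**Working it through.** The plan gives no numerical target for the primary percentage, so there is no figure to reproduce. Participant counts, event counts and the lag are not in the documents and are assumed below.

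**1. Denominator.** Participants who start Off-Treatment are of two kinds. Those dosed later already qualify through the one-dose rule. The added SAP sentence can therefore change the set only by admitting those never dosed. Under SAP 3.5.1 a TEAE needs a first dose date, which they lack.

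Let x be participants with a TEAE, N the SAP safety set and u the never-dosed. The SAP percentage is x/N and the protocol percentage is x/(N − u). Their ratio is 1 − u/N.

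| Assumed x, N, u | SAP set | Dosed only |
|---|---|---|
| 3, 10, 2 | 30.0% (exact 95% CI 6.7 to 65.2) | 37.5% (8.5 to 75.5) |
| 8, 150, 15 | 5.3% | 5.9% |
| 8, 150, 30 | 5.3% | 6.7% |
| 8, 150, 45 | 5.3% | 7.6% |

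The last three rows use the planned 150 participants and an event frequency near the 5.6% for application site reactions in Protocol 2.3.1.

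**2. Window.** I take end of study to be the participant's own follow-up contact, 28 to 35 days after the Week 52/EOT/ET visit (Schedule of Activities). I assume a lag of 28 days, the minimum AE collection time after last dose in Protocol 8.3.1.

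- *Dosed up to EOT/ET:* the gap is (28 to 35) − 28 = 0 to 7 days. It is one day more if the last dose is counted from the evening before the visit.
- *Dosed in cycle 1 only, Off-Treatment in cycles 2 and 3, early termination at Week 12:* last dose plus lag ends at Week 4 with no lag, or at Week 4 + 4 = Week 8 with 28 days. End of study falls at Week 12 + 4 to 5 = Week 16 to 17. The gap is 8 to 9 weeks with the 28-day lag.
- *Design as written, dosing ending on Day 28, full follow-up:* the windows end at Day 28 + 28 = 56 and at Day 365 + 28 = 393, a gap of 337 days. This shows what the rule allows. It is not a case expected in the terminated study, because SAP version 2 (7 January 2021) is dated only 232 days after the protocol (20 May 2020).

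**3. Interval (minor).** For an assumed 0/10, the upper 95% limit is 30.8% by Clopper-Pearson and 27.8% by Wilson. For 1/10 the intervals are 0.3% to 44.5% and 1.8% to 40.4%. The choice of method is visible but does not change the message.

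**4. Exposure-adjusted rate (minor).** An assumed 10 participants followed for 12 weeks give 10 × 12/52 = 2.31 person-years, ignoring censoring at first event. Three events are 3/2.31 = 130 per 100 person-years, exact Poisson 95% CI 27 to 380. If the hazard is front-loaded (assumed 2.0 per person-year for 4 weeks, then 0.5), the rate falls from 200 per 100 person-years at Week 4 to 79 at Week 24. Over the same time the percentage rises from 14.3% to 29.3%. The rate is therefore imprecise, and it also depends on length of follow-up when events come early, as Protocol 2.3.1 reports for application site pain.

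**The case against.** The added sentence in SAP Section 4 is explicit and may be deliberate, or may only clarify that late starters belong. In the second case it adds nobody. It bites only for participants who are Clear at entry and never start treatment, and their number is unknown. Most participants may be dosed close to their last visit, where the two windows nearly coincide. There is also a good reason not to stop at last dose plus a lag: Protocol 4.3 includes Off-Treatment cycles in order to study long-term safety close to clinical practice, and a short window would drop events arising then. All of this stands. It limits the likely size and shapes the fix, but it does not settle which set or which window the tables will use.

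A reader might infer that the SAP broke the protocol by dropping a required primary analysis. The documents do not support that. The rates follow the words for an example in Protocol 9.4.2, and the SAP sentence is equally open-ended. The SAP may modify the protocol, and only major changes to the primary analysis need an amendment. The termination reason in the version history is not tied to the rates, and SAP version 1 is not available, so neither the time of nor the reason for the omission can be established.

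A reader might also infer that the percentages will appear with no account of exposure. SAP 6.5.3 plans duration of treatment, number of applications, amount used, and On- and Off-Treatment cycles. That is not person-time to first event, but it covers most of the need. Nor can one say that an unsuitable interval will be used: none is named, and the sponsor's reporting standard may specify one.

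**Conclusion.** The point holds for the denominator and the window; both need correcting because either can change the primary percentage. The SAP set understates the percentage among dosed participants by the factor 1 − u/N. In the assumed cases that means 30.0% against 37.5%, or 5.3% against 5.9% to 7.6%. The two window ends differ by about 0 to 7 days for participants dosed to EOT/ET under an assumed 28-day lag, and by weeks or more for those Off-Treatment at the end. The actual sample size, the number never dosed and the lag are not given, so these are illustrations and not estimates of the error in the study's results.

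The missing level and method for the safety interval and the unexplained absence of the exposure-adjusted rate are minor clarifications. No hypothesis is tested, so no error rate or power is affected.

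**What to change.** 1. **SAP 4, 6.1.1 and 6.6.1:** base TEAE percentages on participants dosed in this study, as in Protocol 9.3. Report the number never dosed, and any AEs or SAEs they have, separately.
2. **SAP 3.5.1:** replace the two window ends with one that has a numeric end. If last dose plus a lag is chosen, give the lag in days and list AEs after it up to end of study separately, so that Off-Treatment events are not lost.
3. **SAP 6 and 6.1.1 (minor):** state a two-sided 95% exact (Clopper-Pearson) interval for the safety percentages.
4. **SAP 6 or the version history (minor):** either report the exposure-adjusted rate with its person-years beside the 6.5.3 summaries, noting its imprecision and its dependence on follow-up if events cluster early, or record why it was dropped.

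The cost is SAP wording, one extra listing and, if the rate is kept, a few table columns. Dosing and AE dates are already collected, so no new data are needed.

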6.1. Primary Endpoint(s)

6.1.1. Primary Analysis

- Analysis Set: Safety analysis set (see [Section 4](#)).

- Analysis Methodology: Descriptive statistics (see [Section 5.2](#)) for incidence of TEAEs and SAEs

6.2. Secondary Endpoint(s)

Not applicable.

6.3. Other Endpoint(s)

6.3.1. Efficacy Endpoints

6.3.1.1. % Change from Baseline in EASI Over Time

- Analysis Set: FAS (see [Section 4](#)).
- Analysis Methodology: Descriptive statistics (see [Section 5.2](#)) and 95% two-sided confidence intervals for the mean for observed data and % change from baseline in EASI over time

6.3.1.2. Achievement of EASI50 ($\geq 50\%$ improvement from baseline) Over Time

- Analysis Set: FAS (see [Section 4](#)).
- Analysis Methodology: Descriptive statistics (see [Section 5.2](#)) and 95% two-sided confidence intervals for the proportion of participants with EASI50 ($\geq 50\%$ improvement from baseline) over time.

6.3.1.3. Achievement of EASI75 ($\geq 75\%$ improvement from baseline) Over Time

- Analysis Set: FAS (see [Section 4](#)).
- Analysis Methodology: Descriptive statistics (see [Section 5.2](#)) and 95% two-sided confidence intervals for the proportion of participants with EASI75 ($\geq 75\%$ improvement from baseline) over time.

6.3.1.4. Change from Baseline in Treatable %BSA Over Time

- Analysis Set: FAS (see [Section 4](#)).
- Analysis Methodology: Descriptive statistics (see [Section 5.2](#)) and 95% two-sided confidence intervals for the mean for observed data and change from baseline in Treatable %BSA over time.

6.3.1.5. Achievement of Success in ISGA [defined as an ISGA score of Clear (0) or Almost Clear (1) with at least a 2-grade improvement from baseline] Over Time

- Analysis Set: FAS (see [Section 4](#)).

- Analysis Methodology: Descriptive statistics (see [Section 5.2](#)) and 95% two-sided confidence intervals for the proportion of participants with success in ISGA [defined as an ISGA score of Clear (0) or Almost Clear (1) with at least a 2-grade improvement from baseline] over time. Categorical summary (see [Section 5.2](#)) in ISGA will also be reported.

6.3.1.6. Achievement of Improvement in ISGA [defined as an ISGA score of Clear (0) or Almost Clear (1)] Over Time

- Analysis Set: FAS (see [Section 4](#)).
- Analysis Methodology: Descriptive statistics (see [Section 5.2](#)) and 95% two-sided confidence intervals for the proportion of participants with improvement in ISGA [defined as an ISGA score of Clear (0) or Almost Clear (1)] over time.

6.3.1.7. Achievement of Success in Regional ISGA-face [defined as a Regional ISGA-face score of Clear (0) or Almost Clear (1) with at least a 2-grade improvement from baseline] Over Time

- Analysis Set: FAS (see [Section 4](#)).
- Analysis Methodology: Descriptive statistics (see [Section 5.2](#)) and 95% two-sided confidence intervals for the proportion of participants with success in Regional ISGA-face [defined as a Regional ISGA-face score of Clear (0) or Almost Clear (1) with at least a 2-grade improvement from baseline] over time. Categorical summary (see [Section 5.2](#)) in Regional ISGA-face will also be reported.

6.3.1.8. Achievement of Improvement in Regional ISGA-face [defined as a Regional ISGA-face score of Clear (0) or Almost Clear (1)] Over Time

- Analysis Set: FAS (see [Section 4](#)).
- Analysis Methodology: Descriptive statistics (see [Section 5.2](#)) and 95% two-sided confidence intervals for the proportion of participants with improvement in Regional ISGA-face [defined as a Regional ISGA-face score of Clear (0) or Almost Clear (1)] over time.

6.3.1.9. Incidence of the Use of Rescue Medication (topical corticosteroids or topical calcineurin inhibitors)

- Analysis Set: FAS (see [Section 4](#)).
- Analysis Methodology: Descriptive statistics (see [Section 5.2](#)) and 95% two-sided confidence intervals for incidence of the use of rescue medication (topical corticosteroids or topical calcineurin inhibitors).

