6.5.4. Concomitant Medications and Nondrug Treatments

Concomitant drug and non-drug treatment will be summarized according to CaPs. Number of days when rescue medication is taken will be descriptively summarized for All-Treatment Period, respectively.

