9. APPENDICES

Appendix 1. Definition and Use of Visit Windows in Reporting

Visit windows will be used for efficacy and patient/observer reported outcomes variables that display or summarize by study visit.

Visit Label	Target Day	Definition [Day window relative to Study C3291027 Day 1]
Screening/Baseline of qualifying parent study		
Week 4	29	Days 16 to 43
Week 8	57	Days 44 to 71
Week 12	85	Days 72 to 99
Week 16	113	Days 100 to 127
Week 20	141	Days 128 to 155
Week 24	169	Days 156 to 183
Week 28	197	Days 184 to 211
Week 32	225	Days 212 to 239
Week 36	253	Days 240 to 267
Week 40	281	Days 268 to 295
Week 44	309	Days 296 to 323
Week 48	337	Days 324 to 351
Week 52	365	Days 352 to

If two or more visits fall into the same window, keep the one closest to the Target Day. If two visits are equaled distant from the Target Day in absolute value, the later visit should be used.

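### By-visit EASI, ISGA and Regional ISGA-face response is reported only as observed, so threshold-meeting scores on or soon after topical rescue count as response, and no by-visit rescue display is specified.

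*SAP*

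**What the plan says.** **Analysis.** SAP 6.3.1.2 and 6.3.1.3 (EASI50, EASI75) and 6.3.1.5 to 6.3.1.8 (ISGA and Regional ISGA-face, success and improvement) each specify descriptive statistics and a confidence interval over time in the full analysis set. For example, 6.3.1.5 plans "95% two-sided confidence intervals for the proportion of participants with success in ISGA" and 6.3.1.6 plans "95% two-sided confidence intervals for the proportion of participants with improvement in ISGA". None says how to treat a visit affected by rescue.

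**General rules.** SAP 5.3 deals only with absent data: "In general, for analyses using descriptive statistics, missing values will not be imputed". SAP 6 states: "There is no pre-specified estimand for the efficacy and patient/observer reported outcomes evaluation". SAP Appendix 1 chooses between visits by timing alone: "If two or more visits fall into the same window, keep the one closest to the Target Day".

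**Rescue.** Under protocol 6.5.3, a participant with ISGA above 1 may stop crisaborole and use a topical corticosteroid and/or calcineurin inhibitor for up to 28 days, then restart. Crisaborole and rescue may not be used together. Continuous use beyond 28 days leads to discontinuation. Protocol 6.1.1 also allows rescue to be prescribed directly for a flare in an Off-Treatment Cycle.

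**Rescue reporting.** SAP 6.3.1.9 plans "95% two-sided confidence intervals for incidence of the use of rescue medication", the only efficacy endpoint not defined over time. SAP 6.5.4 adds: "Number of days when rescue medication is taken will be descriptively summarized for All-Treatment Period".

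**Status.** These endpoints are exploratory and untested. SAP version 2 followed study termination and revised some analyses "due to the small sample size and the short exposure period".

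**The concern.** The exploratory objective is to describe how well crisaborole works over the long term, and there is no comparator arm. The rescue criterion (ISGA above 1) is the exact complement of the improvement endpoint (ISGA 0 or 1). Rescue is thus offered to participants who are non-responders on that scale, crisaborole is withheld, and a good result with the rescue drug is then tabulated as response.

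A reader of a by-visit proportion cannot tell how much of it was scored during or soon after treatment with another active topical. Overall incidence and total rescue days do not help, because neither is tied to a visit.

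**Working it through.** The documents give no rescue rate, response rate or power figure for these endpoints, so there is no stated result to reproduce. Two things can be checked: whether rescue can reach the by-visit tables, and how far the proportion could move under stated assumptions.

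**1. Timing**

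Inputs: visits every 28 days with a window of ±7 days (protocol 1.3; target days in SAP Appendix 1); rescue of up to 28 days (protocol 6.5.3).

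- Gap between consecutive visits: 28 − 14 = 14 days to 28 + 14 = 42 days.
- A full course begun at a scheduled visit covers days 0 to 27. It is still running at the next visit if the gap is 14 to 27 days. It ended 1 day before a visit at 28 days, 8 days before one at 35 and 15 days before one at 42.
- A full course begun s days after a visit (s = 1 to 27) runs to day s + 27, which is day 28 or later. It therefore covers the next on-time visit.
- For shorter courses with a start spread evenly over the cycle, the chance of covering an on-time visit is L/28: 25% for 7 days, 50% for 14, 75% for 21.

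Rescue can therefore reach the tables either as current use or as very recent use. A flag for use on the visit day alone would miss the full course that ended the day before an on-time visit.

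**2. Size**

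Let r be the share of participants flagged at a visit, c the share of those at ISGA 0 or 1, and p0 the share of unflagged participants at ISGA 0 or 1. All three are assumptions.

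- As observed: (1 − r)p0 + rc
- Flagged visits as non-response: (1 − r)p0
- Flagged visits excluded: p0

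As observed minus non-response = rc:
- r = 5%, c = 30%: 0.05 × 0.30 = 1.5 points
- r = 20%, c = 70%: 0.20 × 0.70 = 14 points

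For ISGA success the gap cannot exceed that for improvement, because every success is also an improvement.

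As observed minus exclusion = r(c − p0):
- p0 = 40%: 0.20 × (0.30 − 0.40) = −2 points; 0.20 × (0.70 − 0.40) = +6 points
- p0 = 60%: 0.20 × (0.30 − 0.60) = −6 points
- p0 = 30%: 0.20 × (0.70 − 0.30) = +8 points

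So against exclusion the difference runs from −6 to +8 points, and its sign depends on whether c is below or above p0.

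**3. Whole participants at the planned size**

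Take 150 participants with 15 flagged (10%), 8 of those responding, and 68 responders among the other 135 (about 50%).
- As observed: (68 + 8)/150 = 76/150 = 50.7% (exact 95% CI 42.4 to 58.9)
- Flagged as non-response: 68/150 = 45.3% (exact 95% CI 37.2 to 53.7)

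**4. Small sample**

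Under the non-response rule, one flagged responder moves the proportion by 100/n points: 10 at an assumed n of 10, 5 at n of 20, 0.67 at n of 150.

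**The case against.** The strongest defence is that as-observed reporting is a legitimate treatment-policy summary. Permitted rescue followed by restart is part of the regimen studied. Protocol 4.3 says the design is meant to resemble everyday practice, although that sentence is about the Off-Treatment Cycle rather than rescue. The documents openly declare no estimand, and efficacy is descriptive with no test. This stands, and is why the as-observed rows should stay. It does not explain why they are the only rows, or why they are not labelled.

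Two stronger readings are tempting, and the documents support neither.

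- *Every score on or after rescue counts as response.* The SAP says nothing of the kind. Scores are taken as they are, and only those meeting the threshold count. Rescue starts from ISGA above 1, so some of these scores will lower the proportion.
- *Rescue use is unreported.* Overall incidence with a confidence interval and total days are both planned. Concomitant treatments follow a sponsor standard that is not reproduced in the SAP and might show dates. What can be said is that the SAP specifies no by-visit rescue display.

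The supplementary row can also be criticised, fairly. It fails a participant who used rescue for a few days early in a cycle, restarted crisaborole and then responded. It also fails a participant whose Off-Treatment flare was treated directly with rescue, a flare crisaborole was never used on. The row is not a crisaborole-only estimate.

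Finally, the range in points is a product of assumed rates, and 14 is its extreme corner. With a very small sample the range is only a guide: at n = 10, a 5% flag rate is half a participant, and confidence intervals will be wide whichever rule is used.

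**Conclusion.** The point holds as a cheap improvement of low impact. Followed as written, the plan counts a threshold-meeting score on or shortly after topical rescue as response in the tables meant to characterise crisaborole, and specifies nothing that shows a reader which visits are affected.

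The size cannot be derived from the documents. The 1.5 to 14 points against a non-response rule rest on an assumed 5% to 20% flagged and 30% to 70% of those at ISGA 0 or 1. A reader might infer that the planned tables overstate crisaborole's effect. That is not established: the gap against a non-response rule cannot be negative by construction, while against excluding the visits the sign is open (−6 to +8 points with p0 between 30% and 60%).

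The consequence is confined to interpreting exploratory efficacy tables in a terminated study with a small sample. The incidence of treatment-emergent and serious adverse events is not affected.

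**What to change.** In SAP 6.3.1.2, 6.3.1.3 and 6.3.1.5 to 6.3.1.8:

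1. Keep the as-observed rows and label them 'regardless of rescue'.
2. At each visit, show the number of participants with non-scalp rescue at the visit or since the previous scheduled visit.
3. Add one supplementary row counting those visits as non-response. State that it is conservative for the two reasons given above. By the formulas it lies at or below both the as-observed and the exclusion figures, so it should be read as a lower bound.

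Derive the flag from the recorded rescue prescription (protocol 6.5.3) and from the dates and reason for use (protocol 6.5). Dates alone will not do: topical corticosteroids and calcineurin inhibitors are allowed on the scalp without time limit (protocol 6.1.1), and ISGA, EASI and treatable %BSA exclude the scalp (protocol 8.1.2, 8.1.3, 8.1.5).

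Optional: show EASI % change (6.3.1.1) and treatable %BSA (6.3.1.4) with and without the flagged visits, and note in SAP 6.5.3 how many Off-Treatment Cycles were entered on rescue.

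Cost: a SAP edit, one derived variable and a few table rows. No new data are needed, and SAP 6.3.1.9 and 6.5.4 already depend on identifying rescue use.
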